7.1. Table of Events

| Procedure | | Visit 0 screening (online/phone) | Visit 1 Baseline (from day after Visit 0 to +14 days) | Visit 2 (day after Visit 1) | Visit 3 (day after Visit 2) | Visit 4 (telephone; 5 days after Visit 2) | Visit 5 (6-9 days after Visit 2) | Visit 6 (day after Visit 5) | Visit 7 (telephone; 5 days after Visit 5) |
|--------------------------|---|----------------------------------|---|-----------------------------|-----------------------------|---|----------------------------------|-----------------------------|--|
| Recruitment | Informed consent | X (oral) | X (written) | | | | | | |
| | Eligibility assessments | X | X | | | | | | |
| | Enrollment and randomization | | X | | | | | | |
| Eligibility assessments | At least 4 hours of initial sleep-EEG | | | x | | | | | |
| | No epileptiform discharges in baseline-EEG | | x | | | | x | | |
| | No psychotropic treatment/illegal drugs within the last 3 months, no alcohol within the last 24 hours | | | x | x | | x | x | |
| Intervention | (Control) Stimulation | | | x | | | x | | |
| | Cognitive testing ¹ | | | x | x | x (only verbal memory and associative verbal memory recall) | x | x | x (only verbal and associative verbal memory recall) |
| | Sleep-EEG ² | | x (next night) | x (next night) | | | x (next night) | | |
| | Actigraphy | | x | x | x | x | x | x | |
| | TMS Motor Thresholding | | | x | | | | | |
| Patient Reported Outcome | Subjective tolerability of sleep EEG | | | x | x | | | x | |
| | Sleepiness (Karolinska Scale) | | | x | x | | x | x | |
| | Sleep quality | | | x | x | | x | x | |
| | Affect (PANAS) | | | x | x | | x | x | |
| Safety Monitoring | Assessment of AEs | | | x | x | x | x | x | x |

¹ Standardized results of: RAVLT (Rey Auditory Verbal Learning Test) (26), word association test, Letter Fluency (28), Stroop Color and Word Test (29), Trail Making Test A and B (30), TAP (Test of Attentional Performance) (31).

² Device worn (yes/no), hours of recording, sleep latency, sleep efficiency, amount of sleep spindles and slow wave sleep.

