| | 
WHEREAS OUR PREVIOUS DESIGN ONLY ALLOWED TO DRAW CONCLUSIONS ABOUT THE EFFECT OF STIMULATION IN GENERAL. THUS, WE NOW USE A CONTROL FREQUENCY OF 21Hz INSTEAD OF THE ACTIVE SHAM STIMULATION.
 
3. tACS AMPLITUDE IS INDIVIDUALIZED (SAME AMPLITUDE FOR BOTH CONDITIONS; HAS TO BE SUPPORTED FOR 1h, THRESHOLDING FOR 21 AND 40 Hz, LOWER AMPLITUDE IS TAKEN)
 
4. NO INDIVIDUALIZED GAMMA, BECAUSE NO CLEAR/SINGLE PEAK DURING RVDLT ACCORDING TO [name]'S ANALYSIS
 
5. ELECTRODE POSITIONING FOR LEAST SIDE EFFECTS: T7/8, P7/8
 
6. ACTIGRAPHY ADDED TO SEE IF STIMULATION CHANGES ACTIVITY PATTERN. TEXT FROM MODIFICATION: ACTIGRAPHY: WEARING AN ACTIGRAPHY WRISTBAND. PARTICIPANTS ARE ASKED TO WEAR A WRIST-WORN ACCELEROMETER FROM VISIT 1 TO VISIT 6. THE DEVICE RECORDS REST AND ACTIVITY PHASES BY MEANS OF AN ACCELEROMETER, THUS ALLOWING CONCLUSIONS TO BE DRAWN ABOUT THE SLEEP-WAKE RHYTHM. WE PURSUE AN ADDITIONAL EXPLORATORY GOAL WITH ADDING ACTIGRAPHY: SUPPLEMENTAL DATA IN ADDITION TO THE ALREADY APPROVED EEG WITH REGARDS TO THE NEUROPHYSIOLOGY OF MEMORY CONSOLIDATION SLEEP AFTER 40 Hz STIMULATION (COMPARED TO 21Hz AND COMPARED TO NIGHTS WITHOUT STIMULATION IN BETWEEN): THE DEVICE IS WORN ON THE WRIST (LIKE A WATCH), IT IS LIGHTWEIGHT, AND IT DOES NOT NEED TO BE RECHARGED DURING THE SCHEDULED WEARING PERIOD.
 
7. MOTOR THRESHOLDING (TEXT FROM MODIFICATION): SINCE THE ORIGINAL DESIGN OF THE STUDY, NEW EVIDENCE SUGGESTS AN INTERESTING RELATIONSHIP BETWEEN THE EFFECT OF tACS AND BRAIN EXCITABILITY MEASURED WITH SINGLE PULSE TMS. WE WILL THEREFORE MEASURE CORTICAL EXCITABILITY BY PERFORMING MOTOR THRESHOLDING USING SINGLE PULSE TMS (TRANSCRANIAL MAGNETIC STIMULATION) DURING VISIT 2. THE PROCEDURE TAKES ONLY A FEW MINUTES, AND ONLY SINGLE PULSES WILL BE APPLIED UNTIL A MOTOR RESPONSE RESULTS AT THE HAND (=5 OUT OF 10 EVOKED POTENTIALS OF FIRST DORSAL INTEROSSEUS MUSCLE =50mV PEAK-TO-PEAK).
 
8. (PLANNING) PREGNANCY IS REASON FOR EXCLUSION
 | |
|--|--|--|

| | | | |
|------------|--|--|--|
| 1.3 | | ADAPTED OUTCOMES TO THE VERSION SUBMITTED TO THE IRB (=ADDING AIM 8). CHANGING TYPOS IN THE SCHEDULE. | |
| 1.4 | | - EXCLUSION CRITERIA: PSQI > 5 (INSTEAD OF >6) - SESSIONS: 8AM-12PM, 12PM-6PM | |

Table of Contents

| | |
|---|----|
| Table of Version Changes | 2 |
| Statement of Compliance | 7 |
| Table of Abbreviations | 8 |
| 1. Protocol Synopsis | 9 |
| 2. Introduction | 12 |
| 2.1. Background Information | 12 |

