| Title | Effects of Transcranial Alternating Current Stimulation (tACS) on Memory Recall and Sleep-EEG in Healthy Elderly Participants (SUPERCHARGE) |
| Study Description | 
The purpose of this clinical trial is to investigate the feasibility and efficacy of non-invasive transcranial alternating current stimulation (tACS) at gamma frequency in enhancing memory recall and modulating sleep network dynamics measured by at-home electroencephalography (EEG) in healthy elderly people. Eligible participants will first collect sleep EEG at home for one night to acclimate to the data collection during sleep. Participants are then randomized into first undergoing either gamma-tACS or control tACS. Stimulation is administered in the lab during a cognitive testing battery that includes memorizing items. After a night of sleep with EEG at home, participants return to the lab the following day to measure memory recall. Memory recall is tested again by telephone five days later. This sequence of encoding during stimulation in the lab, sleep EEG at home for one night, and memory recall is then repeated for the other stimulation condition about a week later. An actigraphy watch (accelerometer) is worn during the whole study period.
 |

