| Aim 7: To investigate whether there is a correlation between motor activity level and stimulation | Effect of stimulation on motor activity level | Correlation between changes in the amount of motor activity the day after stimulation versus the day before; (a) after stimulation in general and (b) after gamma- versus control stimulation. | Exploratory investigation of correlations (Pearson's) between the day before and after the (respective) stimulations. |
| Aim 7: To investigate whether there is a correlation between the TMS motor threshold and the tolerated tACS amplitude (based on subjective symptoms) | Association between TMS motor threshold and symptoms from tACS | Correlation between the level of TMS motor threshold and the highest tolerated tACS level (21Hz and 40Hz, lower value). | Exploratory investigations of correlations (Pearson's) between the measures (% and mA). |

4. Study Design

This is a single-center prospective interventional pilot study with a controlled crossover-design. Each participant is exposed once to the intervention (tACS) and once to the control intervention (control tACS) to allow not only an interindividual but also an intraindividual comparison of outcomes under both conditions. Thus, each participant can serve as their own control.

First, an online prescreening (in REDCap) is performed, where basic eligibility information and informed consent for a screening by telephone is obtained. If, in the subsequent phone screen, inclusion/exclusion criteria are met and the participant provide verbal consent, a meeting on site (UNC Chapel Hill) will be arranged, where participants will sign informed consent and undergo baseline assessments (day 1). Afterwards, participants will receive the single-channel EEG for the following night (night 1). The next day (day 2), the intervention (gamma-tACS or control tACS) during cognitive testing will take place. During the following night (night 2) the EEG will be worn again for recording of sleep EEG at home. The follow-up cognitive testing will be scheduled for the day after (day 3), and again for the fifth day after stimulation (memory recall by telephone).

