This procedure will be repeated for the respective other intervention (gamma-tACS or control tACS) one week (5-9 days) later. Each participant will be wearing an actigraph (accelerometer wristband) during the study period. Additionally, we will perform motor thresholding by TMS on day 2. Additionally, TMS motor thresholding will take place during day 2.

Centralized services are not used. All data (including baseline assessment, cognitive testing results) are stored in a REDCap database.

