| Trail Making Test A and B (30) | Interval (sec), ratio (errors) | D1A, D2A, D1B, D2B | Aim 6 | Secondary outcome |
| Test of Attentional Performance (TAP) (31) | Interval, ratio (Alertness: Percentile rank of median reaction time for correct responses, percentile rank of standard deviation; Go/NoGo: Percentile rank of median reaction time for correct responses, percentile rank of standard deviation, percentile rank of errors; Divided Attention: Percentile rank of median reaction time for correct responses, percentile rank of standard deviation, percentile rank of errors, percentile rank of omissions; Visual Scanning: Percentile rank of median of critical and non-critical, respective standard deviation, omissions) | D1A, D2A, D1B, D2B | Aim 6 | Secondary outcome |
| Sleep EEG | | | | |
| First night with ≥4 hours of recording | Binary (hh:mm) | N1 | Aim 3 | Primary outcome; early termination of study participation if <4 hours |
| EEG worn for ≥4h hours in 3/3 nights | Binary (nights) | N1, N2A, N2B | Aim 3 | Primary outcome |

| | | | | |
|---|-------------------------------------|--------------------|--------------|---------------------|
| Sleep latency | Minutes | N1, N2A, N2B | Aim 4, Aim 5 | Covariate use |
| Sleep efficiency | % | N1, N2A, N2B | Aim 4, Aim 5 | Covariate use |
| Sleep spindles, slow wave sleep | Amount/hour | N1, N2A, N2B | Aim 4, Aim 5 | Primary outcome |
| Subjective tolerability of headband | Binary, nominal | N1, N2A, N2B | Aim 3 | Exploratory use |
| Actigraphy | | | | |
| Motor activity/24 hours, resting time for sleep | %, hours | N2A, D2A, N2B, D2B | Aim 7 | Exploratory outcome |
| Thresholding | | | | |
| TMS motor threshold | % MSO (maximal stimulator output) | D2A | Aim 8 | Exploratory outcome |
| tACS thresholding | mA (lower value of 21 Hz and 40 Hz) | D2A | Aim 8 | Exploratory outcome |
| Safety Monitoring | | | | |
| AEs and SAEs documentation | Events | All | All | Safety monitoring |

¹ Units of measurement or the scale.

² Occasions of evaluation or retrieval:

S = Screening

0 = Enrollment and Baseline

N1 = Night 1

D1A = Day 1 in Intervention A

N2A = Night 2 in Intervention A

D2A = Day 2 in Intervention A

PA = Phonecall in Intervention A

D1B = Day 1 in Intervention B

N2B = Night 2 in Intervention B

D2B = Day 2 in Intervention B

PB = Phonecall in Intervention B

³ The specific aims in which the variable will play a role in data analyses.

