7.3. Enrollment

Visits 0 and 1

The following procedures will occur:

1. Signing of informed consent
2. Completion of demographics and supplementary questions (mainly providing information about the cognitive state): Sex, racial/ethnic categories, education, living conditions, work status, clubs/social organizations, sports, social contacts, media consumption, concomitant medications list, caffeine consumption, alcohol consumption, smoking status.
3. Specific questionnaires to exclude patients with indications for a sleep disorder, depression, anxiety disorder, cognitive impairment, epilepsy:
 - 3.1 Sleep Quality Assessment PSQI (15): Screening for sleep disorders. Result: 0-21 points. Exclusion if >5 points.
 - 3.2 Patient Health Questionnaire-9 (16): Screening for depression. Result: 0-27 points. Exclusion if ≥5 points.
 - 3.3. General Anxiety Disorder-7 (17): Screening for anxiety disorder. Result: 0-21 points. Exclusion if ≥10 points.
 - 3.4. Montreal Cognitive Assessment (MoCA): Screening for dementia. Result: 0-30. Exclusion if <26.
4. Complementary questionnaires to complete patient profile:
 - 4.1 Handedness Questionnaire (22)
 - 4.2 Behavioral Inhibition and Behavioral Activation Self Report Scales (BIS/BAS) (23): These scales are used to monitor the perceived sensitivity to reward and punishment. BIS/BAS is broken into four sub-scores: BIS (7 to 28), BAS drive (4-16), BAS fun-seeking (4-16), and BAS reward (7-20).
 - 4.3 Basic sleep habits (bedtime, sleep latency, wakefulness during the night, waking time, total amount of sleep on average, optimal total amount of sleep)
5. The following instructions will be given for the night and following day:
 - 851 How to use the EEG-headband the night before visit 2 (oral and written instructions, including sleep diary); how to use the actigraphy watch.
 - 5.2 To not consume more caffeine than usually. To please not drink alcohol.
6. The participant will be randomized to the respective intervention for visit 2 (either gamma-tACS or first control stimulation).

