Visit 5 (6-9 days after Visit 2; afternoon/early evening, i.e. start between 12pm and 6pm)

The day before: reminder (e-mail/SMS/phone call, depending on the participant's preference) of appointment on the following day - including request to abstain from alcohol and drugs as well as from excessive caffeine consumption.

1. Questioning whether there has been any use of alcohol, psychotropic substances or illicit drugs during the past 24 hours. If yes, the participant is excluded.
2. Questioning if there is a new diagnosis. If yes, the participant will be excluded if the diagnosis meets exclusion criteria.
3. Questions to assess current sleepiness and mood, as this may affect the results of further testing:
 - 3.1 Questions for sleep quality the night before
 - 3.2 Karolinska Sleepiness Scale
 - 3.3 Positive And Negative Affect Schedule (PANAS)
4. Gamma-tACS or controlstimulation (according to randomization) during the following cognitive tests, presented on a computer screen (2 minutes of resting EEG without stimulation after each test):
 - 4.1 Rey Auditory Verbal Learning Test (RAVLT, version 2)
 - 4.2 Letter Fluency; letters F, A, S

- 4.3 Stroop Color and Word Test
- 4.4 Trail Making Test A and B
- 4.5. Word association test; version 2
- 4.6 Four subtests of the Test of Attentional Performance (TAP): Alertness, Go/NoGo, Divided Attention, Visual Scanning
- 4.7 RAVLT delayed recall; version 2
5. Evaluation of side effects with open question (“Did you feel anything particular or note anything special during this session?”)
6. The participant will be given the sleep diary for the third night with the EEG headband.

Visit 6 (day after Visit 5; morning, i.e. start between 8am and 12pm)

1. The participant brings back the EEG-headband (used the night before). Data quality check, review of sleep diary.
2. Questioning whether there has been any use of alcohol, psychotropic substances or illicit drugs during the past 24 hours. If yes, the participant is excluded.
3. Questions to assess current sleepiness and mood, as this may affect the results of further testing:
 - 3.1 Questions for sleep quality the night before
 - 3.2 Karolinska Sleepiness Scale
 - 3.3 Positive And Negative Affect Schedule (PANAS)
4. Cognitive follow-up testing
 - 4.1 RAVLT “ultra-delayed” recall; version 2
 - 4.2 Letter fluency; letters B, H, R
 - 4.3 Stroop Color and Word Test (SCWT)
 - 4.4 Trail Making Test Part A and B
 - 4.5 Word association recall; version 2

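### If the actigraphy watch comes off at Visit 6, as the Table of Events suggests, Aim 7 compares a full day after the first stimulation with a part day after the second

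*Combined protocol and SAP*

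**What the plan says.** **Wear period.** The actigraphy row of section 7.1 reads "Actigraphy | | x | x | x | x | x | x": blank at Visit 0, marked at Visits 1 to 6, blank at Visit 7. The version 1.2 entry in the Table of Version Changes records the same span: "PARTICIPANTS ARE ASKED TO WEAR A WRIST-WORN ACCELEROMETER FROM VISIT 1 TO VISIT 6". The synopsis is broader: "An actigraphy watch (accelerometer) is worn during the whole study period". Section 4 says "Each participant will be wearing an actigraph (accelerometer wristband) during the study period", without an end point. Section 7.3 puts the instruction on "how to use the actigraphy watch" at enrolment, for the night before Visit 2. The Visit 6 text in section 7.4 has the EEG headband handed back and does not mention the watch.

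**Timing.** Both stimulation visits (2 and 5) start between noon and 6pm. The last on-site visit is "Visit 6 (day after Visit 5; morning, i.e. start between 8am and 12pm". Visit 7 is by telephone. No clock time is given for Visit 1.

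**Outcome.** For Aim 7, the table of measures in section 3 specifies "Correlation between changes in the amount of motor activity the day after stimulation versus the day before", for stimulation in general and for gamma against control. Table 1 (section 4.3) lists "Motor activity/24 hours, resting time for sleep", in percent and hours, on the night and day after each condition. It lists no occasion before stimulation. Neither place says whether a day is a calendar day or a 24-hour window. Section 8.3 plans Pearson correlations for individuals and for the group, labels them exploratory, and states no period or order term for this aim.

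**The concern.** A before-after or gamma-control comparison of daily activity needs windows of the same length and the same mix of day and night. On the schedule in section 7.1 the record stops on the morning after the second stimulation but continues for days after the first. The day after the second session would then be mostly night, with little waking activity in it. Expressing activity as a percentage does not repair this, because a night-weighted window has a different activity share from a full day.

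At stake is whether a lower value after the second session reflects stimulation or only an earlier end of recording. Daytime activity that was not recorded cannot be recovered at analysis.

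**Working it through.** The plan gives no wear-time figure for Aim 7, so there is none to reproduce. The check is clock arithmetic on the visit windows in section 7.4, assuming that wear ends at the start of Visit 6.

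1. **Day after the second stimulation, calendar day.** Recorded from 00:00 to the start of Visit 6 (08:00 to 12:00): 8 to 12 of 24 hours. Assume a 16-hour waking day that begins at 6, 7 or 8am. The waking share recorded runs from 0 (wake at 8am, visit at 8am) to (12 − 6)/16 = 38% (wake at 6am, visit at noon).

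2. **Same day as a window from stimulation.** Start of Visit 5 to start of Visit 6:
   - shortest: 24 + 8 − 18 = 14 h;
   - longest: 24 + 12 − 12 = 24 h.

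   Subtracting the roughly 40-minute session of section 6 gives 13.3 to 23.3 h. With the one hour given in the synopsis it is 13 to 23 h. Set-up before stimulation would shorten it further. If the watch came off at the end of Visit 6, the length of that visit (not stated) would be added. Even in the noon-to-noon case, with a 40-minute session, a complete 24 hours would need 24 − 23.3 = 0.7 h more.

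3. **Day after the first and day before the second stimulation.** Visit 5 is 6 to 9 days after Visit 2, so the interval between visit starts is 6 × 24 + 12 − 18 = 138 h to 9 × 24 + 18 − 12 = 222 h. Both days are complete. With the 5-day minimum given in section 4 it is 5 × 24 + 12 − 18 = 114 h, and the conclusion is the same.

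4. **Day before the first stimulation.** The calendar day of Visit 1 is always partial: a watch put on at 10:00 covers 14 h of it, at 16:00 it covers 8 h. The time available before Visit 2 depends on when the watch goes on:
   - at 10:00: 26 to 32 h;
   - at 12:00: 24 to 30 h;
   - at 16:00: 20 to 26 h.

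   A complete 24-hour window before Visit 2 is impossible only if the watch goes on after 18:00.

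5. **Effect on gamma against control.** Let D be the mean activity lost from the second-period day, and let k of 28 completers receive gamma first. The gamma-minus-control difference is shifted by +D in those k and by −D in the other 28 − k. The shift in the group mean is D × (2k − 28)/28:
   - 14:14 gives 0;
   - 16:12 gives 4/28 = 14% of D;
   - 17:11 gives 6/28 = 21% of D.

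   The direction depends on which sequence is larger. Section 4.2 specifies simple randomisation. Treating the 28 completers as fair coin tosses, the exact binomial gives P(14:14) = 0.15, P(16:12 or more unequal) = 0.57 and P(17:11 or more unequal) = 0.34.

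6. **Contrasts that balance does not protect.** Each individual difference carries the full +D or −D. The session 2 before-after change sets a complete day before against a truncated day after in every participant, whatever the sequence.

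**The case against.** The strongest reply is that removal at Visit 6 is inferred. The row in section 7.1 has no end time, only the headband is named as returned, and the synopsis wording can be read as wear to the end of participation. The documents do not say that the table takes precedence. This stands, so the finding is conditional on wear ending at Visit 6. It does not remove the need for a change. If the synopsis means wear beyond Visit 6, it disagrees with the table, and a return step after the last on-site visit is missing.

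Three stronger readings are tempting, and the documents do not support them:

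- **That nobody has a full day before the first stimulation.** This is true of a calendar day only. Table 1 uses a 24-hour unit, Visit 1 has no fixed time, and step 4 shows that a complete 24 hours is possible.
- **That the schedule favours or penalises gamma.** The shortfall belongs to the second period, and sequence is randomised. The mean is biased only by the sequence imbalance.
- **That Aim 7 cannot be answered.** Matched clock windows can be formed from data already scheduled. The nights after both stimulations lie inside the wear period, so resting time for sleep is not affected in the same way. The version 1.2 rationale for actigraphy is largely about the sleep-wake rhythm and those nights.

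It is also fair that Aim 7 is exploratory in a feasibility pilot, and that no primary or secondary outcome depends on it.

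**Conclusion.** The point holds conditionally. The wear period is stated inconsistently and the watch's return is not described. If wear ends at Visit 6, every participant has a complete day after the first stimulation and only 8 to 12 calendar hours (about 13 to 23 hours from the end of stimulation) after the second, counted to the start of Visit 6. The consequence is a period effect and added noise in gamma against control, a net bias in the mean of about 14% to 21% of the shortfall at splits of 16:12 to 17:11, and distorted individual contrasts and session 2 before-after change.

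This rests on the section 7.1 schedule being followed and on the waking-day assumption for the 0 to 38% range. The size of D in activity units cannot be derived from the documents. The impact is limited to an exploratory aim and mainly to its daytime activity component. Correction is still worthwhile, because the lost hours cannot be recovered and the remedy is cheap.

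**What to change.** 1. Reconcile section 7.1 with the synopsis and section 4, and state when and how the watch is returned.
2. Preferred: say in section 7.1 and in the Visit 6 text that the watch stays on until at least the end of the Visit 6 calendar day, and for at least 24 hours after stimulation if a 24-hour window is used, with return by mail.
3. Alternative, if the watch must be collected at Visit 6: replace the per-24-hours measure with identical clock windows after each session. Start at the later of the person's two stimulation end times and finish no later than the earlier of the two morning-visit times (Visits 3 and 6).
4. Define the day used in Aim 7. Take the full washout days between Visits 3 and 5 as the no-stimulation reference (4 to 7 days when Visit 5 is 6 to 9 days after Visit 2: 6 − 2 and 9 − 2). Add those occasions to the actigraphy row of Table 1.
5. Include a period term in the gamma-control comparison under either option.

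**Cost.** The preferred option takes about one more day of wear, a later return with some risk of lost watches, and an amendment, which the Statement of Compliance requires the IRB to approve before use. The alternative changes only the outcome and analysis wording, but gives up daytime activity on the day after stimulation.
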